## **MATERIALS AND METHODS**

### ***Study Population and Protocol***

This was a single-center, prospective, assessor-blinded, noninferiority, randomized controlled study conducted at a tertiary referral center (Incheon St. Mary's Hospital, Incheon, Korea). Individuals who underwent colonoscopy with or without esophagogastroduodenoscopy (EGD) for various indications were eligible for inclusion. Study subjects were enrolled between November 2017 and February 2018. Individuals who met all of the following criteria were included: (1) age 40–75 years; (2) American Society of Anesthesiologists (ASA) class I or II; (3) outpatients; and (4) no previous history of bowel resection or gastrectomy. Exclusion criteria were as follows: (1) cancellation, (2) violation of protocol for bowel preparation, such as subjects in the SDD group ingesting a purgative the previous day or as an SPD; or subjects in the SPD group ingesting a purgative the previous day or as an SDD. After informed consent was obtained, study subjects were randomly assigned to the SDD or SPD group. Randomization was performed using a block size of four, stratified by colonoscopy time (morning vs afternoon) and sex, using a computer-generated randomization list.

The protocol for bowel preparation is shown in Figure 1. Subjects underwent bowel preparation at home. Study subjects were encouraged to finish 2 L PEG within 1 h. If ingestion was difficult, 2 L PEG was consumed within 1.5 h. Hence, 2 to 3 h were required to fully ingest the 4 L PEG. Individuals in the SDD group ingested PEG on the day of the colonoscopy. For those who underwent morning colonoscopy, ingestion of 4 L PEG was started at 5 a.m. Individuals who were scheduled to undergo afternoon colonoscopy were instructed to take 2 L PEG starting at 7 a.m., then after a 2-h break, the remaining 2 L PEG was ingested starting at 10 a.m. Individuals in the SPD were instructed to begin ingesting 2 L

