### ***Bowel Cleansing Efficacy, Bowel Movement Kinetics, and Colonoscopy Results***

The primary endpoint of this study was the bowel cleansing efficacy assessed by the Boston bowel preparation scale (BBPS). The BBPS score is the sum of three segmental scores (range 0–9). Each segment is graded on a 4-point scale: 0, inadequate; 1, poor; 2, good; and 3, excellent. The rates of cleansing success, defined as all segments  $\geq 2$  and total BBPS score, were compared between groups. The bowel cleansing efficacy was also assessed by the Aronchick scale, which has scores of excellent, good, fair, poor, and very poor; details of the Aronchick scale are described elsewhere.

Bowel movement kinetics included the number of defecations, the start and finish time of bowel preparation, and the last defecation time. The amount of PEG and additional water ingested were recorded.

The results of the colonoscopy were analyzed. The cecal intubation time, colonoscopy withdrawal time, polyp detection rate (PDR), ADR, and the number of adenomas per patient

were recorded. For those who underwent EGD, fluid in the stomach was suctioned and its volume was measured.

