### ***Statistical Analysis***

We assumed a bowel cleansing success rate for SPD of 85% and set the inferior margin at 10%. With 80% power and a type I error of 0.05, the required sample size for each group was calculated to be 158. A total of 176 subjects in each group was required, considering a 10% drop-out rate. Continuous variables are expressed as mean  $\pm$  standard deviation. Categorical variables are expressed as number and percent. The demographic characteristics, bowel cleansing efficacy, safety profile, tolerability, bowel movement kinetics, and results of colonoscopy were compared between the two groups. For this analysis, we used Student's *t* test for continuous variables, and the chi-square or Fisher's exact test for categorical variables. A *p*-value  $<0.05$  was considered significant. The safety analysis of safety and

tolerability included all subjects except those who were excluded for cancellation or protocol violation. Per-protocol (PP) analysis was used for the patients who completed colonoscopy. Bowel cleansing efficacy and bowel movement kinetics were investigated in the PP analysis. All statistical analyses were conducted using SAS software (9.0; SAS Institute, Cary, NC, USA).

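### The trial is designed and sized as noninferiority with a 10-point margin, but the stated analysis only tests equality and gives no rule for concluding noninferiority

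*Combined protocol and SAP*

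**What the plan says.** Study Population and Protocol calls the trial a "single-center, prospective, assessor-blinded, noninferiority, randomized controlled study". The section on bowel cleansing efficacy opens with "The primary endpoint of this study was the bowel cleansing efficacy assessed by the Boston bowel preparation scale (BBPS". It then says that the success rate (every segment scoring at least 2) "and total BBPS score, were compared between groups".

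The margin appears once, in the sample-size text of Statistical Analysis: "We assumed a bowel cleansing success rate for SPD of 85% and set the inferior margin at 10" per cent. The next sentence reads "With 80% power and a type I error of 0.05, the required sample size for each group was calculated to be 158", and 10% drop-out raises this to 176.

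The same section then describes the analysis: "The demographic characteristics, bowel cleansing efficacy, safety profile, tolerability, bowel movement kinetics, and results of colonoscopy were compared between the two groups". The methods named for this are Student's t test for continuous variables and "the chi-square or Fisher's exact test for categorical variables", with significance at p<0.05. Efficacy is analysed in the per-protocol set.

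**The concern.** A chi-square or Fisher test takes equal success rates as its null hypothesis. Rejecting it shows a difference. Failing to reject it does not show that SDD is less than 10 points worse. Noninferiority needs the opposite null, that SDD is worse by 10 points or more, and evidence against it. The margin is used to size the trial and does not appear in the analysis.

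Two things are at stake. First, p<0.05 is the only criterion in the text, so a reader looking for the success rule may take a non-significant result as noninferiority. Secondly, an interval can be computed later from the group counts, but its level, method and decision rule would not have been fixed in advance. The text does not say whether 0.05 is one- or two-sided, so even the confidence level cannot be read from it.

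**Working it through.** **Inputs.** From Statistical Analysis: SPD success 85%, margin 10%, power 80%, type I error 0.05, 158 per group, 10% drop-out, 176 per group. Assumed because not stated: SDD success also 85%, margin in absolute percentage points, one-sided 0.05.

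**1. Reproduce the sample size.** Noninferiority formula, unpooled variance, equal groups, true difference zero:

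n = 2 × p(1 − p) × (z₁₋α + z₁₋β)² / margin²

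- One-sided 0.05: 2 × 0.85 × 0.15 × (1.645 + 0.842)² / 0.10² = 157.7, so 158. With drop-out, 158 / 0.9 = 175.6, so 176. Both stated figures are matched.
- One-sided 0.025: 200.1, so 201. With drop-out, 201 / 0.9 = 223.3, so 224.
- Margin read as relative (10% of 85% = 8.5 points), one-sided 0.05: 0.255 × 6.183 / 0.085² = 218.2. This does not match.
- Two-sided equality test, 85% against 75%: 250. This does not match.

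The sample size is therefore that of a margin test at one-sided 0.05, which corresponds to a two-sided 90% interval.

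**2. Compare the rules.** I enumerated all pairs of binomial outcomes with 158 per group and SPD at 85%. The chi-square test is uncorrected and two-sided. The ranges cover Wald, Newcombe and Miettinen-Nurminen limits.

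| True SDD rate | p ≥ 0.05 | Lower 90% limit > −10 | Lower 95% limit > −10 |
|---|---|---|---|
| 75% (at the margin) | 39.5% | 5.0–5.2% | 2.4–2.6% |
| 80% | 78.8% | 31.5–32.4% | 20.9–21.7% |
| 85% (equal) | 95.1% | 79.5–80.3% | 68.8–70.0% |

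The probability that a trial is non-significant and also fails the 90% Miettinen-Nurminen rule is 34.6%, 47.4% and 18.0% in the three rows.

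**3. Where the rules part.** Fix SPD at 134/158 (84.8%):

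- Chi-square: p = 0.047 at SDD 120/158 and 0.064 at 121/158, so results are non-significant from 121 (76.6%) upward.
- Miettinen-Nurminen z against −10 points: 1.609 at 129, 1.767 at 130, 1.927 at 131, 2.088 at 132.
- A 90% interval (z above 1.645) therefore passes from 130 (82.3%), and a 95% interval (z above 1.960) from 132 (83.5%). Wald and Newcombe give the same cut-offs.

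Counts of 121 to 129 are non-significant but fail the 90% rule. Under the 95% rule the range is 121 to 131. Counts of 130 and 131 pass at 90% and fail at 95%, so there the level alone decides the conclusion.

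**4. One example.** SDD 122/158 against SPD 134/158: difference 0.772 − 0.848 = −0.076. The standard error is √(0.772 × 0.228/158 + 0.848 × 0.152/158) = 0.0439, and chi-square p = 0.085. The Wald lower limit is −0.076 − 1.645 × 0.0439 = −14.8 points (90%) or −0.076 − 1.960 × 0.0439 = −16.2 points (95%). The result is inconclusive: neither noninferiority nor inferiority beyond 10 points is shown.

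**The case against.** The strongest reply is that this is an omission, not a wrong choice. The sentence on tests is generic: it covers demographics, safety and efficacy together, and nothing says that a non-significant result will be called noninferiority. A noninferiority design with a margin implies an interval, and the counts and percentages allow one to be computed. On this view the 39.5% is a worst case under a reading the authors may never have intended.

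Part of this stands. The 39.5% and 78.8% are conditional on that reading and are not the trial's error rate. The text also shows only that no margin test is described, not what was finally done. But the sentence names cleansing efficacy explicitly among the variables compared by these tests, and an implied interval has no level, method or rule.

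A second reply is that 90% is a preference. The text does not state sidedness, so 95% is also open. The 90% level is inferred, but it is the level whose sample size reproduces both 158 and 176.

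A third reply is that enrolment and analysis are described as already done, so new wording cannot restore prespecification and larger groups are not available. That is right, and it shapes the remedy. It does not remove the need for the interval if noninferiority is to be claimed.

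**Conclusion.** The concern holds and should be fixed before any claim of noninferiority. The stated analysis does not test the hypothesis the trial was sized for, and no criterion for noninferiority is given. This conclusion rests on the text alone and needs no numerical assumption.

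The size of the possible error does rest on assumptions: SPD at 85%, 158 analysed per group, and p ≥ 0.05 taken as success. Then the false noninferiority rate at the margin is about 40%, against about 5% for the rule that matches the sample size. The sample-size arithmetic is sound; the fault is the mismatch between it and the analysis.

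**What to change.** Add to Statistical Analysis: *The primary analysis is the difference in cleansing success rate (all BBPS segments at least 2), SDD minus SPD, in the per-protocol set, with a two-sided 90% Miettinen-Nurminen confidence interval, equivalent to the one-sided 0.05 test used for the sample size. Noninferiority is declared only if the lower limit is above −10 percentage points.*

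Also:

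- State in the sample-size sentence that the type I error is one-sided, the margin is absolute and SDD is assumed to be 85%.
- Name one interval method. Newcombe is equally acceptable.
- State that total BBPS, which has no margin, and the Aronchick scale are supportive. Keep equality tests for secondary outcomes, or for superiority once noninferiority is shown.
- Unless a dated earlier plan fixes the level, say that it was set afterwards and report both the 90% and 95% intervals.

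**Cost.** This needs a few sentences and one interval. At 90%, no extra patients are needed: power at 158 per group is 79.5% (Miettinen-Nurminen) or 80.0% (Newcombe). If 95% is preferred, power at 158 is about 69–70%. Keeping 80% would have needed 201 per group (224 with drop-out), which cannot be obtained if enrolment is closed, so the lower power should then be reported. Noninferiority becomes harder to reach than a non-significant p-value, and one-sided 0.05 is the more lenient of the two levels, which should be stated openly.

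### Randomisation is stratified by colonoscopy time and sex, but the outcome tests ignore both factors; if the factors are prognostic, the tests are mildly conservative and lose a little precision

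*Combined protocol and SAP*

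**What the plan says.** Under Study Population and Protocol, the combined document states: "Randomization was performed using a block size of four", "stratified by colonoscopy time (morning vs afternoon) and sex". Two binary factors give four strata, and a block of four with two arms implies 1:1 allocation within each.

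Under Statistical Analysis, the scope of testing is broad: "The demographic characteristics, bowel cleansing efficacy, safety profile, tolerability, bowel movement kinetics, and results of colonoscopy were compared between the two groups". For these comparisons "we used Student's *t* test for continuous variables" and "the chi-square or Fisher's exact test for categorical variables". No stratified test, regression model or covariate is named anywhere.

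The design parameters are in the same section: SPD success of 85%, a 10-point margin, and "With 80% power and a type I error of 0.05", giving 158 per group and 176 after allowing for 10% drop-out.

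**The concern.** Blocking within strata forces the arms to be nearly equal on colonoscopy time and sex. Differences between strata then contribute almost nothing to the sampling variation of the group difference. A pooled chi-square, Fisher or t test still counts those differences as noise, so its standard error is too large wherever the strata predict the outcome.

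Colonoscopy time is plausibly prognostic here. The purgative schedule differs by session in both arms, and the outcomes include start and finish times of preparation and time of last defecation, which may depend heavily on session if analysed as clock times. The choice of these two factors for stratification suggests they were thought to matter.

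What is at stake is efficiency and agreement between design and analysis. There is also a secondary point: efficacy is analysed per protocol, after cancellations and regimen violations are removed, so the strata may no longer be exactly balanced. A stratified estimate accounts for that and a pooled one does not. Nothing in the documents allows the size of such imbalance to be estimated.

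**Working it through.** **Inputs from the plan.** Success p = 0.85 in SPD; margin 0.10; power 80%; type I error 0.05, sidedness not stated; n = 158 per group.

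**Assumed inputs.** Equal success in both arms; strata of equal size; the same stratum differences in both arms; the stratum-specific rates themselves. The plan names no test against the margin, so the noninferiority figures assume a lower Wald limit compared with −0.10.

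**1. The plan's own figure.** n = 2p(1−p)(z₀.₉₅ + z₀.₈₀)²/0.10² = 2 × 0.1275 × (1.645 + 0.842)²/0.01 = 157.7, so 158. Then 158/0.90 = 175.6, so 176. Both reproduce with one-sided 5%. One-sided 2.5% would need 201.

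**2. Standard errors for cleansing success.** Unstratified: √(2p(1−p)/n). Under stratum-balanced allocation: √(2[p(1−p) − B]/n), where B is the between-stratum variance of the success rates. The unstratified value is √(2 × 0.1275/158) = 4.02 points throughout.

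| Assumed rates | B | Stratified SE (points) | Ratio of SEs | Actual size, nominal two-sided 5% |
|---|---|---|---|---|
| No stratum effect | 0 | 4.02 | 1.000 | 5.0% |
| One factor, 80/90% | 0.05² = 0.0025 | 3.98 | 1.010 | 4.8% |
| Two factors, ±5 points each | 0.0050 | 3.94 | 1.020 | 4.6% |
| One factor, 75/95% | 0.10² = 0.0100 | 3.86 | 1.042 | 4.1% |
| Extreme, 70/100% | 0.15² = 0.0225 | 3.65 | 1.102 | 3.1% |

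The size is 2[1 − Φ(1.96 × ratio)]. Simulation of the 75/95% case gave a mean unstratified SE of 4.01 points against an actual SD of 3.87, and 4.0% rejection.

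**3. Noninferiority power at n = 158, normal approximation.** Unstratified: Φ[(0.10 − z·SE_unstratified)/SE_stratified]. Stratified: Φ[0.10/SE_stratified − z].

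- One-sided 5%, 80/90%: 80.3% against 80.8%, a gap of just under 0.5 points.
- One-sided 5%, 75/95%: 81.0% against 82.9%, a gap of about 1.8 points.
- One-sided 2.5%: the same formulas with z = 1.96 give gaps of 0.7 and 2.7 points.

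Simulation with 40 patients per group per stratum gives slightly smaller gaps at one-sided 5%. At 75/95% the unstratified test has size 4.6% and power 81.6%, against 83.2% stratified (1.6 points). At 80/90% its size is 4.98%, essentially nominal, and the gap is about 0.2 points. The simplest stratified Wald limit ran at about 5.3% instead of 5%, so part of any gain measured with it is not genuine; a better interval is preferable.

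**4. Continuous outcomes.** If session means differ by g within-session SDs and sessions are of equal size, the between-session variance is g²/4 and the t test's SE is too large by √(1 + g²/4). With 158 per group the correct SE is √(2/158) = 0.1125 SD. The power column uses an illustrative 0.3 SD effect.

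| g | SE ratio | Actual size, nominal 5% | Power, t test against adjusted |
|---|---|---|---|
| 0.25 | 1.008 | 4.8% | 75.5% against 76.0% |
| 0.5 | 1.031 | 4.3% | 74.1% against 76.0% |
| 1 | 1.118 | 2.8% | 68% against 76% |

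**The case against.** The strongest reply is that this hardly matters for the primary endpoint. No stratum-specific rate is given, so every size above is an assumption. At 80/90% the loss is a fraction of a point and the test is at its nominal level for practical purposes. That stands. The 1 SD continuous case is also the far end of the range, and the trial is not powered on any continuous outcome.

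A reader might infer that the benefit of stratifying is thrown away. The figures do not support this. Stratified allocation lowers the true variance of the pooled estimate whichever test is used: in step 3, unstratified power at n = 158 rises from 80.1% with no stratum effect to 81.0% at 75/95%. Planned power of 80% is kept, and the loss is only relative to a better analysis.

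A reader might also infer that the tests always run below their nominal level. That depends on prognostic strength, which is unknown. If stratum effects ran in opposite directions in the two arms and cancelled, the excess variance would vanish.

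Finally, the plan states no confidence interval or test against the margin. That is a separate and larger gap. Stratifying is a refinement of whatever margin analysis is specified, and does not depend on how that gap is filled.

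**Conclusion.** The mismatch between stratified randomisation and unstratified outcome tests is in the text and is worth correcting. Its consequence is mild and conditional. For cleansing success, with assumed session rates of 80/90% to 75/95%, the standard error is about 1 to 4% too large and the power loss is about 0.2 to 1.6 points at one-sided 5% (0.7 to 2.7 at one-sided 2.5%). For continuous outcomes the effect depends on how far session means lie apart, and becomes appreciable only near 1 SD.

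The error is conservative. It would be wrong to read it as a threat to a noninferiority conclusion, because it makes the margin harder to meet. It would be equally wrong to call the trial underpowered on this account. The mechanism is certain; its size in this trial is not, because the documents do not say how strongly either factor predicts any outcome.

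**What to change.** Amend the test sentence in Statistical Analysis for outcome comparisons only. Baseline demographics should be left out, since comparing sex within strata of sex has no meaning.

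- **Cleansing success:** Mantel-Haenszel risk difference stratified by colonoscopy time and sex, with a stratified Miettinen-Nurminen or Newcombe confidence interval compared with the 10-point margin.
- **Other categorical outcomes:** Cochran-Mantel-Haenszel test with the same four strata, and an exact stratified version when events are sparse, as may happen with individual adverse events.
- **Continuous outcomes:** linear model with group, colonoscopy time and sex.

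Only the two stratification factors are needed. Other covariates such as age are a separate choice that this point does not support.

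The cost is a few sentences of plan text, some additional SAS code, and 2 to 3 degrees of freedom. It needs no new data, and the sample size stays at 158 per group (176 with drop-out).

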PEG at 9 p.m., 1 day before the colonoscopy. The remaining 2 L PEG was ingested from 7 a.m. for morning colonoscopy or from 10 a.m. for afternoon colonoscopy. We encouraged the participants to ingest additional water until their bowel effluent was clear. Consumption of fibers and seeds was restricted for 2 days before colonoscopy. Soft food was allowed for dinner the day before colonoscopy. Colonoscopy was performed between 10 a.m. and 5 p.m. (morning colonoscopy 10 a.m.–12 p.m.; afternoon colonoscopy 1:30 p.m.–5 p.m.) by three board-certified colonoscopists with experience of more than 2000 cases. The colonoscopists were blinded to the bowel cleansing regimen. This study was approved by the Institutional Review Board of Incheon St. Mary's Hospital and registered at ClinicalTrials.gov (NCT03315949).

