### ***Safety and Tolerability***

The composite safety profile included vital signs and questionnaire findings. Vital signs were checked on the day of randomization and at colonoscopy. Before the colonoscopy, all study subjects completed a questionnaire asking about adverse events, tolerability, and bowel movement kinetics. The questionnaire contained the following items: (1) adverse events related to the ingestion of the purgative; (2) number of sleep disturbances during the night before colonoscopy; (3) overall satisfaction with the bowel cleansing regimen (very satisfied, satisfied, intermediate, dissatisfied, very dissatisfied); and (4) willingness to use the bowel preparation regimen again. The patients used a checklist of possible adverse events to report whether they had experienced any of the following during or after ingestion of the bowel cleanser: nausea, vomiting, bloating, abdominal pain, dizziness, headache, and/or any other symptoms.

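### Protocol violators, a group that can be identified only after randomisation, are left out of the safety and tolerability analysis

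*Combined protocol and SAP*

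**What the plan says.** Statistical Analysis states that the analysis of safety and "tolerability included all subjects except those who were excluded for cancellation or protocol violation". It describes no other safety population, such as everyone who took any purgative.

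Study Population and Protocol lists cancellation and violation of the preparation protocol as exclusion criteria. It illustrates violation separately for each arm. In the SDD group (all PEG on the day of colonoscopy) it is intake on the previous day or in the SPD pattern. For the SPD group (PEG split between the evening before and the day itself) the text reads "or subjects in the SPD group ingesting a purgative the previous day or as an SDD". The same section says "After informed consent was obtained, study subjects were randomly assigned to the SDD or SPD group", and that preparation took place at home.

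Safety and Tolerability says: "Before the colonoscopy, all study subjects completed a questionnaire asking about adverse events, tolerability, and bowel movement kinetics". The items include adverse events, sleep disturbance, satisfaction, and "willingness to use the bowel preparation regimen again".

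For efficacy and bowel movement kinetics, Statistical Analysis says "Per-protocol (PP) analysis was used for the patients who completed colonoscopy". It does not mention adherence there.

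**The concern.** A criterion that needs both the allocated arm and the intake that followed cannot be an eligibility screen. It removes people who were randomised and took a purgative, and it removes them under a different rule in each arm. The safety and tolerability comparison is then no longer between the groups as randomised.

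This matters most for tolerability. Whether people can follow and accept a schedule is part of what the questionnaire measures, and those who did not follow it are the ones left out. If their number, their symptoms or their satisfaction differ between arms, the reported difference shifts. Safety and tolerability are not the primary endpoint, so the stake is the credibility of the secondary comparison.

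**Working it through.** **1. The plan's own figures.** Inputs from Statistical Analysis: success rate 85%, margin 10 points, power 80%, type I error 0.05, drop-out 10%. With 0.05 taken as one-sided:

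n = (1.645 + 0.842)² × 2 × 0.85 × 0.15 / 0.10² = 157.7, so 158 per group.

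158 / 0.90 = 175.6, so 176 per group.

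Both reproduce, and neither changes if violators stay in the safety set. The plan adds "A total of 176 subjects in each group was required, considering a 10% drop-out rate", an allowance of 176 − 158 = 18 per arm (18/176 = 10.2%). It is not split between cancellations and violations. So 18 is the most that the allowance covers; it is not an estimate of violators who attended.

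**2. Order of events.** Consent, randomisation, intake at home, questionnaire, colonoscopy. Violation is fixed at the intake step, after randomisation. The questionnaire comes after intake, so a violator who attended could complete it. A subject who cancelled may have no questionnaire, and the point is not pressed for those subjects.

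**3. One-arm effect of leaving violators out.** Let k of 176 subjects with data be violators, f = k/176, q the event rate in retained subjects and v the rate in violators. The rate in all subjects is (1 − f)q + fv and the analysed rate is q, so the understatement is f(v − q). The documents give none of k, q or v; all values below are assumed, with q = 20%.

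| k | f | v = 10% | v = 20% | v = 50% | v = 80% |
|---|---|---|---|---|---|
| 4 | 2.27% | −0.2 | 0 | 0.7 | 1.4 |
| 9 | 5.11% | −0.5 | 0 | 1.5 | 3.1 |
| 18 | 10.23% | −1.0 | 0 | 3.1 | 6.1 |

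Entries are percentage points; a negative value means that the arm's rate is overstated. Example: 9/176 × (0.50 − 0.20) = 0.0153.

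**4. Effect on the comparison.** The shift in the difference is f₁(v₁ − q₁) − f₂(v₂ − q₂). With 9 violators in one arm and 4 in the other, and v = 50% and q = 20% in both, it is 1.53 − 0.68 = 0.85 points. With 9 in each arm it is 0.

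**5. Scale.** The standard error of a difference at 20% with 158 per arm is √(2 × 0.2 × 0.8 / 158) = 4.5 points. Among the one-arm shifts in the table, only 18 violators at 80% exceeds it.

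**6. Violation wording for SPD.** Read literally, intake on the previous day is a violation for an SPD subject, yet that schedule begins with 2 L of "PEG at 9 p.m., 1 day before the colonoscopy". The sentence distinguishes three patterns: previous day, split, and same day. The probable meaning is therefore the whole amount on the previous day, but the available text does not say so. The figure that shows the protocol is not reproduced in the text reviewed.

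**The case against.** The strongest objection concerns the mechanism. Most listed violations happen before any dose of the assigned schedule. An SDD subject who drinks the evening before has not yet started the assigned regimen, and an SPD subject who drinks only on the day has skipped its start. Such departures cannot be reactions to adverse events of the assigned regimen. Only an SPD subject who took everything the previous day could have begun as assigned. This stands: intolerance is a possible reason, not an established one. The list is open-ended, and anticipated inconvenience could still drive departures.

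Second, no passage expressly says that violators' questionnaires were kept. All study subjects may already mean a restricted group. This also stands, and the fix asks for the number with data.

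Third, violators took a different pattern, so analysis by assigned group alone would attribute effects of one pattern to the other arm. This is a fair criticism, and it is why a supporting analysis by pattern followed is needed.

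Fourth, violation is listed as a study-level exclusion, so violators are probably outside the per-protocol set already. That is likely, and one explicit sentence would settle it.

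A reader might infer more than the documents support:

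- **That compliant SPD subjects were excluded.** Nothing shows this, and the probable reading of the wording rules it out.
- **That the noninferiority comparison is compromised by this rule.** The rule quoted governs safety and tolerability. Any effect on efficacy would be of unknown size and is not claimed.
- **That about 18 violators per arm were expected.** That figure covers all drop-out.

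**Conclusion.** The concern holds in limited form. The plan leaves protocol violators out of the safety and tolerability analysis on a criterion that arises only after randomisation and differs by arm, and it offers no all-exposed alternative. This can bias the comparison if departures, or outcomes among those who depart, differ between arms.

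Neither size nor direction can be determined from the documents. The illustration runs from a small overstatement, through zero, to a 6.1-point understatement in one arm. It rests wholly on assumed rates and counts, and similar departures in both arms would partly or fully cancel. It also assumes that violators who attended completed the questionnaire, which is the direct reading of Safety and Tolerability but is not stated for violators by name.

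This should be corrected, but it does not touch the sample size. The SPD wording and the silence on violators in the per-protocol definition are minor clarifications, with no effect under their probable readings.

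**What to change.** 1. Analyse safety and tolerability in all randomised subjects who took any purgative and have questionnaire data, by assigned group, whether or not they violated the preparation protocol.
2. Add a supporting analysis by the intake pattern actually followed. Under Bowel Cleansing Efficacy, Bowel Movement Kinetics, and Colonoscopy Results, the plan already records start and finish times and the amount of PEG, which allow the pattern to be classified.
3. Report by arm the number of violators and how many have questionnaire data. If their questionnaires were not kept, say so as a limitation.
4. State whether violators are excluded from the per-protocol set.
5. Reconcile the SPD violation wording in Study Population and Protocol with the SPD schedule in the same section. No change to either regimen is proposed.

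The cost is slightly more analysis work and a few sentences. No further patients or visits are needed, and no new data if violators' questionnaires were kept. The assigned-group analysis will mix intake patterns to some extent; the supporting analysis addresses that.
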